5.4. Scientific Rationale for Study Design

Study AMBU is an open-label, Phase 2 study to evaluate the safety, PK, PD, and clinical response of mirikizumab in pediatric patients with UC, to provide data for dose regimen confirmation in Phase 3.

An open-label study ensures that all patients receive active treatment while allowing the primary evaluation of PK of mirikizumab treatment in pediatric patients.

The 12-week IV dosing induction period was chosen CCI

CCI The 40-week maintenance period enables CCI The timing of the induction and maintenance endpoints was chosen based on characterization of the safety and efficacy of mirikizumab through 52 weeks of continuous treatment in Study AMAC, the Phase 2, placebo-controlled, double-blind adult clinical trial of mirikizumab in moderately to severely active UC, as well as consistency with the timing of the induction and maintenance endpoints of the ongoing Phase 3 adult program studies AMAN and AMBG.

Patients are allowed to continue non-biologic background therapy throughout the study (for example, 5-aminosalicylic acids [5-ASAs], corticosteroids, AZAs, and 6-MPs), subject to concomitant medication and dose stabilization criteria. In this context, it is anticipated that mirikizumab will be administered as an add-on therapy in the majority of patients.

The selection of clinical remission at Week 52 using MMS (FDA 2016) and the Pediatric Ulcerative Colitis Activity Index (PUCAI) as secondary endpoints are consistent with regulatory guidance documents (EMA 2016a,b). These endpoints will assess improvement in the clinical signs and symptoms of stool frequency (SF), rectal bleeding (RB), and abdominal pain, and

additionally assess the visual appearance of the mucosa through the endoscopic subscore (ES).

CCI

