6.1. Inclusion Criteria

Patients are eligible to be included in the study only if they meet all of the following criteria within the screening period, which is CCI [REDACTED], unless otherwise specified below:

Informed Consent

- [1] Have given assent (if appropriate) with parent/legal guardian signed informed consent approved by the ethical review board (ERB) governing the site.

Patient Characteristics

[figure not shown]
- [2] Male or female patients weighing >10 kg AND ≥ 2 and <18 years of age at the time of informed consent.

[2a]

CCI [REDACTED]

[2b]

CCI [REDACTED]

[3] Both the parent or legal representative and child (if capable) must agree to comply with the requirements of the protocol.

[4] CCI [Redacted]

Type of Patient and Disease Characteristics

[5] Have an established diagnosis of UC of ≥ 3 months in duration before baseline, CCI [Redacted]

[6] Have moderately to severely active UC as defined by a CCI [Redacted] within CCI [Redacted] before first dose of study treatment (baseline).

[7] Have evidence of UC extending proximal to the rectum CCI [Redacted]

Prior Medication Failure Criteria

[8] Patients must have an inadequate response to, loss of response to, or intolerance to at least 1 of the medications described in Criteria [8a] OR [8b]. **Documentation of dose, frequency, route of administration, and duration of the prior failed treatment is required.**

[8a] **Biologic-naive patients:** Patients who have an inadequate response to, loss of response to, or are intolerant to at least 1 of the following medications:

- Corticosteroids
 - Corticosteroid-refractory colitis, defined as signs and/or symptoms of active UC despite a CCI [REDACTED]

CCI [REDACTED]

CCI [REDACTED]

- Immunomodulators:
 - Signs and/or symptoms of persistently active disease despite at least 3 months' treatment with 1 of the following:

- Oral AZA CCI [REDACTED] or 6-MP CCI [REDACTED], or

CCI [REDACTED]

- History of intolerance to at least 1 immunomodulator CCI [REDACTED]

Discontinuation despite clinical benefit does not qualify as having failed or being intolerant to UC non-biologic therapy.

[8b] **Biologic/JAK inhibitor-experienced patients:** Patients who have an inadequate response to, CCI [REDACTED] to biologic therapy for UC (such as anti-TNF antibodies or anti CCI [REDACTED] antibodies) and/or to JAK inhibitors (such as tofacitinib), as described below.

Investigators must document an adequate trial of the medication.

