Prior failured of a JAKg inhibitor	No	Ever, Never
Prior corticosteroid failured	No	Ever, Never
Prior immunomodulator	NI	·
failure ^{d, h}	No	Ever, Never
Baseline UC Therapies		
Baseline corticosteroid useh	No	Yes, No
Baseline prednisone equivalent dose	Yes	None
Budesonide MMX	No	Yes, No
Baseline immunomodulator use ^h	No	Yes, No
Baseline corticosteroid and immunomodulator useh	No	Corticosteroid only, Immunomodulator, Neither, Both
Baseline use of oral aminosalicilatesi	No	Yes, No
Baseline use of methotrexateh	No	Yes, No
Baseline use of thiopurineh	No	Yes, No
Baseline Disease Characteristics		
Duration of UCi	Yes	<1 year, ≥ 1 to <3 years, ≥ 3 year to <7 years, ≥ 7 years
Age at Diagnosis of UCk	Yes	$<6, \ge 6$ to <10 year, ≥ 10 to <17 years
Historical Disease Severity	No	Ever Severe, Never Severe
Baseline Disease Extent	No	Ulcerative proctitis (rectum), Left-sided (descending or sigmoid colon), Extensive (transverse colon), Pancolitis (cecum or ascending colon)
Baseline Fecal Calprotectin	Yes	≤250 μg/g, >250 μg/g
Baseline C-reactive Protein (CRP)	Yes	≤6 mg/L, >6 mg/L
Baseline Modified Mayo Score	Yes	Moderate (4-6), Severe (7-9)
Baseline Total Mayo Score	Yes	Moderate (6-9), Severe (10-12)
Baseline Partial Mayo Score	Yes	None
Baseline Endoscopic Mayo Subcore	No	Possible values of 4-point scale in Table AMBU.6.4
Baseline Stool Frequency Mayo Subscore	No	Possible values of 4-point scale in Table AMBU.6.4
Baseline Rectal Bleeding Mayo Subscore	No	Possible values of 4-point scale in Table AMBU.6.4
Baseline PGA Mayo Subscore	No	Possible values of 4-point scale in Table AMBU.6.4
Baseline PUCAI	No	Severe (65-85), Moderate (35-60), Mild (10-30), None (<10)
CCI		
Baseline Abdominal Pain NRS	Yes	<4,≥4
Baseline Patient's Global Rating of Severity (PGRS)	Yes	None
Baseline Nocturnal Stool	Yes	Yes (≥1), No (0)
Baseline Bristol Stool Scale	No	Not Loose Stool (1 – 3), Loose Stool (4-5)

Abbreviations: ATC = Anatomical Therapeutic Chemical; BMI = body mass index; DOB = date of birth; eCRF = electronic case report form; JAK = Janus kinase; NRS = numeric rating scale; PGA = Physician's Global Assessment; PUCAI = Pediatric Ulcerative Colitis Activity Index; TNF = tumor necrosis factor; UC = ulcerative colitis

- ^a Age in years will be calculated as length of the time interval from the DOB to the informed consent date.
- b Body mass index (BMI) will be calculated as: $BMI(kg/m^2) = Weight(kg)/(Height(m))^2$.

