- ^c Biologic systemic therapies include: adalimumab, adalimumab biosimilar, alemtuzumab, brazikumab, certolizumab, golimumab, guselkumab, infliximab, infliximab biosimilar, interferon therapy, other TNF biosimilar, risankizumab, rituximab, tildrakizumab, ustekinumab, vedolizumab, visilizumab, tofacitinib, and other JAK inhibitors. For the purpose of counting the number of prior biologics, adalimumab and adalimumab biosimilar will be counted as one biologic
- d Failure defined as reasons for prior treatment discontinuation are: loss of response, inadequate response or intolerance to medication.
- e Anti-TNF alpha biologics include: infliximab, infliximab biosimilar, adalimumab, adalimumab biosimilar, golimumab, certolizumab pegol.
- f Possible anti-integrin treatments include vedolizumab.
- g Options on the prior medications eCRF for JAK inhibitors include: tofacitinib and other JAK inhibitor.
- h ATC codes for immunomodulators including methotrexate and thiopurines are listed in the compound level safety standards.
- i Aminosalicilates will be defined using ATC code A07EC (all members).
- j Length of the interval from the date of UC diagnosis to the date of informed consent.
- k Age at diagnosis in years will be calculated as the time interval from the DOB to the date of UC diagnosis.

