6.9. Prior and Concomitant Therapy

Medications will be classified into Anatomical Therapeutic Chemical drug classes using the latest version of the World Health Organization drug dictionary. Medication start and stop dates will be compared to the date of first dose of treatment in each treatment period to allow medications to be classified as concomitant for each treatment period.

Prior medications are those medications that start and stop prior to the date of first dose of study treatment. *Concomitant medications* are those medications that start before, on, or after the first day of study treatment of the defined treatment period and continue into the treatment period. Concomitant medications are assigned to the treatment period in which they are actually ongoing. For all summary tables of concomitant medications, preferred terms of concomitant medication will be summarized by weight/treatment dose group:

- summary of prior medications for mITT population,
- summary of concomitant medication for mITT population for the Induction and the combined Induction and Maintenance periods, and
- summary of concomitant medication for mITT population within class of interest (corticosteroid therapy, immunomodulatory therapy) for the Induction and the combined Induction and Maintenance periods. The definition of these two classes of interest will be based on compound level safety standards.

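### Footnote d counts corticosteroid and immunomodulator failure only if the drug was stopped, so a child whose only failure in the class is to a drug still being taken is tabulated as never having failed

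*SAP*

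**What the plan says.** **SAP 6.7, Table AMBU.6.3.** The prior-therapy block has two Ever/Never rows for non-biologic failure. One is printed as "Prior corticosteroid failured", where the last letter is the footnote mark. The other begins "Prior immunomodulator" and carries footnotes d and h. Footnote d says: "Failure defined as reasons for prior treatment discontinuation are: loss of response, inadequate response or intolerance to medication".

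**SAP 6.9.** "Prior medications are those medications that start and stop prior to the date of first dose of study treatment". A drug that runs on into the treatment period is classed as concomitant.

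**Protocol 6.1, criterion [8a].** A biologic-naive child can qualify through corticosteroids or through immunomodulators. The corticosteroid route opens "Corticosteroid-refractory colitis, defined as signs and/or symptoms of active UC despite a", and the rest is redacted. The immunomodulator route reads "Signs and/or symptoms of persistently active disease despite at least 3 months' treatment with 1 of the following", followed by a partly redacted list that starts with oral AZA or 6-MP. Intolerance is a further route. In the visible text, discontinuation appears only as a negative rule: stopping a drug that was helping does not count as failure.

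**Continuing therapy.** Criterion [9] admits children on stable doses of permitted drugs, including oral corticosteroids. Protocol 5.4 allows corticosteroids, AZA and 6-MP to continue, and adds that "it is anticipated that mirikizumab will be administered as an add-on therapy in the majority of patients". Appendix 6 lists oral corticosteroids and AZA, 6-MP and MTX as permitted.

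**The concern.** The SAP and the protocol use two different ideas of failure for the same drugs. The protocol asks whether disease stayed active on the drug. The SAP asks why the drug was stopped. The two agree when a failed drug is withdrawn, which is the usual course for biologics. They part company when a child keeps taking the failed drug as background therapy, which the protocol expressly allows.

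At stake is the description of how treatment-refractory the enrolled children are. In a small uncontrolled study, readers rely on the baseline table for that. Rows that miss failures to ongoing therapy understate it, and a subgroup or comparison that used them would carry the same misclassification.

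**Working it through.** The plan gives no figure for this point. The check sets the rules side by side on one case and then scales the effect.

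**1. A worked case.** Take a biologic-naive child with active UC after more than 3 months of AZA. The child enters on a stable AZA dose and has never stopped a corticosteroid or an immunomodulator for failure.

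| Rule | Result for this child |
|---|---|
| Protocol 6.1 [8a], immunomodulator route | Met: active disease despite treatment |
| SAP 6.9, prior medication | AZA is not prior, because it did not stop before first dose |
| Table AMBU.6.3, footnote d, immunomodulator row | No discontinuation reason, so *Never* |
| Table AMBU.6.3, footnote d, corticosteroid row | No discontinuation for failure, so *Never* |
| Table AMBU.6.3, baseline immunomodulator use | *Yes* |

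**2. Consistency check.** The visible text of [8a] names only corticosteroids and immunomodulators. Every child who enters under it has therefore failed at least one of the two classes and should be *Ever* on at least one of the two rows. Footnote d allows *Never* on both.

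**3. Does another row recover the information?** For biologics, the table also has separate rows for inadequate response, loss of response and intolerance, and these do not carry footnote d. Corticosteroids and immunomodulators have only the footnote-d rows.

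**4. Which drugs are exposed?** Appendix 5 requires anti-TNF antibodies, anti-integrin antibodies and JAK inhibitors to be stopped before the screening endoscopy, so failure of those comes with a stop. The same holds for IV and rectal corticosteroids and for cyclosporine, tacrolimus and mycophenolate. The gap is therefore mainly confined to oral corticosteroids and AZA, 6-MP or MTX.

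**5. Which children are exposed?** Only those whose sole failure in the class is to a drug still being taken. One earlier course stopped for non-response or intolerance makes the child *Ever*. Intolerance normally leads to stopping, so it is little affected.

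**6. Size per child.** SAP 5.2 plans about 10 children >40 kg and about 20 children ≤40 kg, so about 30 in all. One misclassified child moves a row by:

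- >40 kg group: 1/10 = 10 percentage points
- all ≤40 kg patients: 1/20 = 5 points
- overall: 1/30 = 3.3 points

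Table AMBU.6.2 splits the ≤40 kg children into two dose groups. The shift within either of those is larger than 5 points, because each holds fewer than 20 children.

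**7. Number of children.** This cannot be derived. It lies between zero and all children whose only failure in a class is to an ongoing drug, and the documents do not count them.

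**The case against.** The strongest reply accepts the wording gap and disputes how much follows from it.

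- **Redacted and unseen material.** Parts of [8a], [9b] and [9c] are redacted, and the eCRF and the compound-level standards are not available. The programming may already capture failure of ongoing drugs. This stands as a limit on confidence about what will be produced. It does not rescue the footnote, which would then misdescribe the table.
- **Number affected.** A reader might infer from the add-on statement in Protocol 5.4 that a large share of the trial is misclassified. For instance, 15 of 30 children biologic-naive with 50–80% continuing the failed drug would give 15 × 0.5 = 7.5 to 15 × 0.8 = 12 children, or 25–40% of 30. The documents support neither input. The add-on statement covers any non-biologic background therapy, including 5-ASA, which the visible text of [8a] does not name. The calculation also ignores earlier stopped courses.
- **Eligibility.** A reader might infer that *Never* on both rows would look like a breach of criterion [8]. Eligibility rests on the documentation that criterion [8] requires, and SAP 6.15 has important deviations identified under a separate plan, not from this table.
- **Subgroups and adult comparisons.** A reader might infer that these are all distorted. SAP 6.14 and Protocol 10.3.7.1 name previous biologic use, not these rows. Subgroup analyses are optional, and only the open-ended wording for further subgroups could reach these rows. Protocol 10.3.5 leaves comparison with adult data to a separate plan, so its use of these rows is unknown.
- **Partial cover.** Baseline use of corticosteroids, immunomodulators, thiopurines and methotrexate is tabulated, so ongoing therapy is visible. It is not labelled as failure, so the failure rows remain wrong as titled.

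**Conclusion.** The point holds in a limited form. By its literal wording, footnote d returns *Never* for a child who failed, and is still taking, an oral corticosteroid or an immunomodulator. An [8a] child can be *Never* on both rows. This is a wrong result under a stated rule, not merely missing detail.

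The size is known only per child, as worked out above; no total can be given. The conclusion rests on the visible text of [8a] and on the derivation following the footnote as written.

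The consequence is descriptive. It reaches two baseline rows and any optional subgroup or comparison built on them. SAP 6.7 plans no inference on baseline characteristics and SAP 6.2 no covariate adjustment. The primary PK analysis, the efficacy endpoints and patients' eligibility do not change. The correction is worth making because it is cheap.

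**What to change.** For the corticosteroid and immunomodulator rows only, give failure its own footnote with two alternatives. A child is *Ever* if either applies:

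1. a prior course was discontinued for inadequate response, loss of response or intolerance (the present rule); or
2. there was inadequate response, loss of response or intolerance to a drug still ongoing at baseline, as documented for criterion [8a] or in the prior-therapy record.

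The second alternative must be added to the first and must not replace it. Criterion [8] needs only one qualifying failure, under [8a] or [8b]. A child who enters through a biologic need not have a corticosteroid or immunomodulator failure documented for that criterion. A definition tied only to criterion [8] could therefore turn true failures in such children into *Never*.

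Leave footnote d unchanged for biologics and JAK inhibitors.

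The cost is one footnote, one derivation change, and a check that the eCRF or source records hold failure status for ongoing drugs. Criterion [8] already requires dose, frequency, route and duration of the failed treatment to be documented, but that does not guarantee an eCRF field for failure.

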6.8. Treatment Compliance

Treatment compliance with investigational product will be summarized for patients who have at least one dose (that is, mITT population) for the Induction Period and for the combined Induction and Maintenance Periods. Treatment compliance for each patient will be calculated as:

```
Treatment\ compliance\ (\%) \\ = 100\ \times \frac{Total\ number\ of\ study\ drug\ administration\ visits}{Total\ number\ of\ study\ drug\ administration\ visits\ planned\ per\ protocol}
```

The "total number of study drug administration visits planned per protocol" is based on the number of planned administration visits before the patient discontinued study drug. Each patient will be defined as having had a study drug administration visit on a given date if:

- For visits where the patient is to receive an IV infusion, they received at least 80% of the planned infusion dose as derived from the infusion electronic case report form (eCRF) page.
- For visits where the patient is to receive SC injections, they received the planned number of injection doses as derived from the injection eCRF page.

"Overall compliance" with therapy is defined as having at least 80% treatment compliance. Patient treatment compliance will be summarized for the mITT population by weight/treatment dose group.

6.9. Prior and Concomitant Therapy

Medications will be classified into Anatomical Therapeutic Chemical drug classes using the latest version of the World Health Organization drug dictionary. Medication start and stop dates will be compared to the date of first dose of treatment in each treatment period to allow medications to be classified as concomitant for each treatment period.

Prior medications are those medications that start and stop prior to the date of first dose of study treatment. *Concomitant medications* are those medications that start before, on, or after the first day of study treatment of the defined treatment period and continue into the treatment period. Concomitant medications are assigned to the treatment period in which they are actually ongoing. For all summary tables of concomitant medications, preferred terms of concomitant medication will be summarized by weight/treatment dose group:

- summary of prior medications for mITT population,
- summary of concomitant medication for mITT population for the Induction and the combined Induction and Maintenance periods, and
- summary of concomitant medication for mITT population within class of interest (corticosteroid therapy, immunomodulatory therapy) for the Induction and the combined Induction and Maintenance periods. The definition of these two classes of interest will be based on compound level safety standards.

6.10. Efficacy Analyses

The description and derivation of the efficacy/health outcomes measure and endpoints are provided in Table AMBU.6.4.

Table AMBU.6.5 provides the detailed analyses including analysis type, method and imputation, population, time point, and dosing regimen comparisons for secondary efficacy/health outcomes analyses. Note that the details of each analysis will follow the general principles described in Section 6.13.

6.10.1. Primary Outcome and Methodology

The primary objective of this study is to evaluate the PK of mirikizumab treatment in pediatric patients. Analysis of primary endpoints is described in separate PK/PD analysis plan as mentioned in Section 6.11.1.

 Table AMBU.6.4.
 Description and Derivation of Efficacy/Health Outcomes Measures and Endpoints

Measure	Description	Variable	Derivation / Comment	Definition of Missing
Mayo Score and components	The Mayo score is a composite instrument to measure Ulcerative Colitis disease activity. It is comprised of the following 4 subscores: Stool Frequency (SF): The SF subscore is a patient-reported measure. This item reports the	SF subscore	Calculated by averaging and rounding the 4-point daily SF subscore over 3 days as described in Appendix 1. Possible values are: (0) Normal number of stools for subject; (1) 1 to 2 stools more than normal; (2) 3 to 4 stools more than normal;	Missing if fewer than 3 available measurements in the relevant 7 days.
	number of stools in a 24-hour period, relative to the normal number of stools for that patient in the same period. The normal reference is collected at baseline/screening. Rectal Bleeding (RB): The RB subscore is a patient-reported measure. This item reports the most severe amount of blood passed for a given day Endoscopic Subscore (ES): The ES	RB subscore	(3) 5 or more stools than normal. Calculated by averaging and rounding the 4-point daily RB subscore over 3 days as described in Appendix 1. Possible values are: (0) No blood seen; (1) Streaks of blood with stool less than half of the time; (2) Obvious blood (more than just streaks) or streaks of blood with stool most of the time; (3) Blood alone passed	Missing if fewer than 3 available measurements in the relevant 7 days.
	is a physician-reported measure that reports the worst appearance of the mucosa on flexible sigmoidoscopy or colonoscopy. Physician's Global Assessment (PGA): The PGA is a physician-reported measure that summarizes the investigator's assessment of the patient's UC disease activity.	ES subscore	Possible values are: (0) Normal or inactive disease; (1) Mild disease (erythema, decreased vascular pattern); (2) Moderate disease (marked erythema, absent vascular pattern, friability, erosions); (3) Severe disease (spontaneous bleeding, ulceration)	Single item. Missing if missing.
	Each subscore is on a 4-point scale, ranging from 0 to 3.	PGA subscore	Possible values are: (0) Normal (1) Mild disease	Single item. Missing if missing.

Measure	Description	Variable	Derivation / Comment	Definition of Missing
			(2) Moderate disease	
			(3) Severe disease	
		Modified Mayo Score	Calculated as: SF + RB + ES.	Missing if SF, RB or ES
		(MMS)		subscores are missing.
		Partial Mayo Score	Calculated as: SF + RB + PGA.	Missing if SF, RB or PGA subscores are missing.
		Alternate MMS Clinical Remission	SF subscore = 0, or SF = 1 with a ≥1-point decrease from baseline, and RB subscore = 0, and ES subscore = 0 or 1 (excluding friability)	Missing if SF, RB, or ES subscores are missing.
		MMS Clinical	SF subscore = 0 or 1	Missing if SF, RB, or ES
		Remission	RB subscore $= 0$, and	subscores are missing.
			ES subscore = 0 or 1 (excluding friability)	J
		MMS Clinical Response	A decrease in the MMS of ≥2 points and ≥30% decrease from baseline, and A decrease of ≥1 point in the RB subscore from baseline or a RB score of 0 or 1	Missing if baseline or Week 12 MMS is missing.
		Endoscopic Remission	ES = 0 or 1 (excluding friability).	Missing if ES is missing.
		Symptomatic Remission	$SF = 0$, or $SF = 1$ with a ≥ 1 -point decrease from baseline and $RB = 0$	Missing if SF or RB is missing.
		Time to first symptomatic remission	For patients who are observed to meet the remission criteria during the Induction Period, time will be from the start of the Induction Period to the first measurement date where the patient met the remission criteria based on weekly averages.	Patients not observed to meet remission criteria during the Induction Period will be censored after the date of their last measurement during the Induction Period.

Measure	Description	Variable	Derivation / Comment	Definition of Missing
			CCI	
		Time to first symptomatic response	For patients who are observed to meet the response criteria during the Induction Period, time will be from the start of the Induction Period to the first measurement date where the patient met the response criteria based on weekly averages.	Patients not observed to meet response criteria during the Induction Period will be censored after the date of their last measurement during the Induction Period.
		Endoscopic subscore of 0	ES = 0.	Missing if ES is missing.
		Total Symptomatic Score	Calculated as SF + RB.	Missing if SF or RB is missing.
		Endoscopic Response	A decrease in the ES of ≥1 point compared to baseline.	Missing if ES is missing.
		SF component of clinical remission	SF = 0, or $SF = 1$	Missing if SF is missing.
		RB component of clinical remission	RB = 0	Missing if RB is missing.
		Corticosteroid-free remission at Week 52	Corticosteroid-free remission without surgery at Week 52, defined as: Clinical remission at Week 52, and No corticosteroid use or UC-related surgery for ≥12 weeks prior to Week 52	NRI if any component is missing.
		Loss of Clinical Response	CCI	

Measure	Description	Variable	Derivation / Comment	Definition of Missing
Urgency NRS	CCI	Urgency NRS Score	Calculated by averaging data from all available diary entries of Urgency NRS for a 7 day period as described in Appendix 1.	Missing if fewer than 4 available measurements in the relevant 7 days (see Appendix 1).
Abdominal Pain NRS	The Abdominal Pain NRS is a single patient-reported item that measures the "worst abdominal pain in the past 24 hours" using a 6-point scale ranging from 0 (no pain) to 5 (worst possible pain) for 8-11 years old, and 11-point NRS ranging from 0 (no pain) to 10 (worst possible pain) for children < 8 years old as completed by a caregiver and those 12-17 years old.	Abdominal Pain NRS Score	Calculated by averaging data from all available diary entries of Abdominal Pain NRS for a 7 day period as described in Appendix 1.	Missing if fewer than 4 available measurements in the relevant 7 days.
PGIC	The Patient's Global Impression of Change (PGIC) scale is a patient-rated instrument designed to assess a patients' rating of change in their symptom(s). Responses are graded on a 7-point Likert scale. Patients or caregivers will record their response on the PGIC electronically as source data in the tablet device at appropriate visits.	PGIC Score	Single Item	Single item, missing if missing. No imputation.
PGRS	Patient's Global Rating of Severity (PGRS) is a 1-item patient-rated questionnaire designed to assess the patients' rating of their disease symptom severity over the past	PGRS Score	Calculated by averaging data from all available diary entries of PGRS for a 7 day period as described in Appendix 1.	Missing if fewer than 4 available measurements in the relevant 7 days.

Measure	Description	Variable	Derivation / Comment	Definition of Missing
	24 hours. Responses are graded on a 6-point scale in which a score of 0 indicates the patient has no symptoms (that is, "none") and a score of 5 indicates that the patient's symptom(s) are "very severe."			
Nocturnal Stool	The Nocturnal Stool instrument is a single item asking the patient to record the number of stools they had during the night (or day, for shift workers) causing them to wake from sleep.	Nocturnal Stool Score	Calculated by averaging data from all available of Mocturnal Stool for a 7 day period as described in Appendix 1.	Missing if fewer than 4 available measurements in the relevant 7 days.
Fatigue NRS	CCI	Fatigue NRS Score	Calculated by averaging data from all available diary entries of Fatigue NRS for a 7 day period as described in Appendix 1.	Missing if fewer than 4 available measurements in the relevant 7 days.
Bristol Stool Scale	The Bristol Stool Scale is a single item that provides a pictoral and verbal description of stool consistency and form ranging from Type 1 (Hard Lumps) to Type 5 (Watery/liquid). An additional option provided was "6. Did not poop."	Bristol Stool Scale score	Calculated by using the worst value (ie, largest number from 1 to 5) from all available diary entries of Bristol Stool Scale for a 7-day period as described in Appendix 1. Responses of "Did not poop," will be counted as missing for that day.	Missing if fewer than 4 available measurements in the relevant 7 days.
		Loose Stool	Bristol Stool Scale score of 4 or 5.	Bristol Stool Scale score is missing
PUCAI	The PUCAI (Turner et al. 2007) is a clinician-administered, 6-item questionnaire that measures: abdominal pain; RB; stool	PUCAI Score	All items are answered as an average over the 'past 2 days'. A total disease activity score is calculated from 0 to 85, with	Missing if any component is missing.

Measure	Description	Variable	Derivation / Comment	Definition of Missing
	consistency; number of stools;		Severe: 65-85	
	nocturnal stools; and activity level		Moderate: 35-60	
	(see Appendix 7 of the protocol).		Mild: 10-30, and	
			None: <10.	
			The clinician will record the patient or	
			caregiver/legal guardian responses for the	
			PUCAI electronically as source data in the	
			tablet device at appropriate visits.	
		PUCAI clinical	PUCAI clinical remission is defined as a	Missing if any component is
		remission	PUCAI score of <10 points	missing.
		PUCAI clinical	PUCAI clinical response is defined as a	Missing if any component is
		response	reduction in baseline PUCAI score of ≥20	missing.
		1	points.	8

Measure	Description	Variable	Derivation / Comment	Definition of Missing
	CCI			
Histo-Endo	Combined histology and endoscopic endpoints.	Histologic-endoscopic mucosal improvement Histologic-endoscopic	Histologic improvement and endoscopic remission. Defined as achieving both histologic	Missing if any component of the definition is missing. Missing if any component of the
		mucosal remission	remission and endoscopic remission	definition is missing.
CRP	C-reactive protein (CRP) is a biomarker of inflammation.	CRP	Lab value. May be transformed if needed.	Single lab value. Missing if missing.
Fecal calprotectin	Fecal calprotectin is used as a biomarker of intestinal inflammation in clinical practice.	Fecal calprotectin	Lab value. May be transformed if needed.	Single lab value. Missing if missing.
Growth and Pubertal Assessments	Occipital head circumference	Head circumference	Occipital head circumference measurements will be performed on patients less than 3 years of age at baseline. Measurements will be taken at baseline and then approximately Q12W thereafter, until the patient reaches the age of 3 years.	Data will be missing for patients who are 3 years or older at entry. Missing if missing.
	Change from baseline in height (cm)	Height CFB	Change from baseline in height (cm) at all study visits. Height is measured 3 times at all visits, height at each visit is calculated	Missing if baseline height or height at visit is missing.

Measure	Description	Variable	Derivation / Comment	Definition of Missing
			using the average of the 3 measurements.	
	Change from baseline in weight (kg)	Weight CFB	Change from baseline in weight (kg) at all study visits.	Missing if baseline weight or weight at visit is missing.
	Height Z-score and percentile by sex and age will be calculated using the CDC growth data shown at: https://www.cdc.gov/nccdphp/dnpao/growthcharts/resources/sas.htm	Height Z-score Height Percentile	Observed height z-score and percentile by sex and age	Missing if height at visit is missing.
	This approach uses a Box-Cox transformation to calculate the height z-score and percentile of the normal distribution for the corresponding age and sex.			
	Height Percentile Change from Baseline	Height Percentile CFB	Change from Baseline is calculated as Present height percentile – Baseline height percentile	Missing if baseline height or height at visit is missing.
	Weight Z-score and percentile by sex and age will be calculated using the CDC growth data shown at: https://www.cdc.gov/nccdphp/dnpao/growthcharts/resources/sas.htm This approach uses a Box-Cox	Weight Z-score Weight Percentile	Observed weight z-score and percentile by sex and age	Missing if weight at visit is missing.
	transformation to calculate the weight z-score and percentile of the normal distribution for the corresponding age and sex.			
	Weight Percentile Change from Baseline	Weight Percentile CFB	Change from Baseline is calculated as Present weight percentile – Baseline weight percentile	Missing if baseline weight or weight at visit is missing.
	Observed height velocity by gender and age group. Age groups for which	Height velocity	Observed height velocity by gender and age group will be calculated at baseline	Data will be missing if either present height or previous height

Measure	Description	Variable	Derivation / Comment	Definition of Missing
	this will be summarized are 2 to <8, 8 to <12, and 12 to <18.		according to the following formula: (Present Height [cm] - Previous Height [cm])/Interval (months) Between Measurements × 12	is missing.
Assessment of Puberty	Total testosterone levels will be collected from male patients ≥9 years of age. Estradiol levels will be collected from female patients ≥9 years of age, until the female begins menstruating. If the patient is 9 years of age and has already begun menstruation, estradiol levels will not be required.	Hormone level	Total testosterone levels for male patients ≥9 years of age and estradiol levels for female patients ≥9 years of age, until the female begins menstruating.	Missing if patients are less than 9 years old or if date of onset of menstruation for females if exists. Missing if missing.
EIMs	Extraintestinal manifestations (EIMs) are collected using the	Baseline EIMs	EIMs ongoing at first dose of study treatment.	No Imputation.
	medical history and adverse event eCRFs. Extraintestinal manifestations include, but are not limited to: uveitis, peripheral arthritis, ankylosing spondylitis, aphthous stomatitis, arthralgia, autoimmune hepatitis, cholelithiasis, deep vein thrombosis, iritis, nephrolithiasis, erythema nodosum, osteopenia, osteoporosis, pancreatitis, sclerosing cholangitis, pyoderma gangrenosum, sacrolitis and skin vasculitis NOS.	Resolution of Baseline EIMs	Complete resolution of baseline EIMs at Week 12 or 52. If a patient has multiple baseline EIMs, then at least one of the EIMs must have resolved.	No Imputation

Abbreviations: CFB = change from baseline; NOS = not otherwise specified; NRI = non-responder imputation; NRS = Numeric Rating Scale; PUCAI = Pediatric Ulcerative Colitis Activity Index; Q12W = every 12 weeks.

 Table AMBU.6.5.
 Description of Secondary Efficacy/Health Outcomes Analyses

		Analysis Method	Population	
Measure	Variable	(Section 6.1.3)	(Section 6.1.1)	Time Point(s)
Mayo Score and components	MMS Clinical Remission	Proportion for each weight/treatment dose group along with the 95% 2-sided CI with NRI and as observed	mITT	Weeks 12 and 52
			mITT who are remitters from	Week 52
			Week 12	
			mITT who are MMS clinical	Week 52
			responders from Week 12	
	MMS Clinical Response	Proportion for each weight/treatment	mITT	Weeks 12 and 52
		dose group along with the 95%	mITT who achieve MMS	Week 52
		2-sided CI with NRI and as observed.	clinical response at Week 12	
	Corticosteroid-free	Proportion for each weight/treatment	mITT	Week 52
	remission	dose group along with the 95%		
		2-sided CI with NRI and as observed.		
	Endoscopic Remission	Proportion for each weight/treatment	mITT;	Weeks 12 and 52
		dose group along with the 95%	mITT who are in endoscopic	Week 52
		2-sided CI with NRI and as observed.	remission at Week 12	
	Endoscopic subscore of 0	Proportion for each weight/treatment	mITT	Weeks 12 and 52
		dose group along with the 95%		
		2-sided CI with NRI and as observed.		
	Symptomatic remission	Proportion for each weight/treatment	mITT	At all scheduled visits
		dose group along with the 95%		
		2-sided CI with NRI and as observed.		
PUCAI	PUCAI clinical remission	Proportion for each weight/treatment	mITT	Weeks 12 and 52
		dose group along with the 95%	mITT who achieve PUCAI	Week 52
		2-sided CI with NRI and as observed.	clinical remission at Week 12	
			mITT who achieve PUCAI	Week 52
			clinical response at Week 12	
